### **Sample size calculation:**

Sample size estimation was based on testing the change in KAP before and after each educational intervention. The predicted sample size was found to be 265 children for each intervention, by assuming an  $\alpha$  level of 0.05,  $\beta$  level of 0.1 (power = 90%), allocation ratio of 1:1, to detect an effect size  $d$  of 0.2. After adding a 20% increase to adjust for dropout, the final sample size was 318 children for each intervention (total sample size = 636 children). Sample size calculation was performed using G\*Power software version 3.1.9.4 for MS Windows, Franz Faul, Kiel University, Germany.

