### **Study procedures:**

- 1) A literature review was conducted using electronic search engines like PubMed and Google scholar to identify studies assessing the effect of online and conventional oral health education on improving the oral health knowledge and practice in school children regarding their oral hygiene.
- 2) After reviewing many articles, a questionnaire was selected to assess the above outcomes. The questionnaire was chosen according to availability and effectiveness, and it was modified by simplifying and deselecting some of the questions that aren't related to the age group to better suit the age group of question.
- 3) A piloting session will be done on two separate classes, one from each educational stage to assess the modified questionnaire in terms of ease of understanding and comprehension to the participants. Those two classes will not be included in the final results of the study.
- 4) The questionnaire will be distributed before conducting the oral health education sessions (both online and conventional) to assess the pre-session knowledge and practice of the participants.
- 5) All questionnaires are self-administered but a well-trained interviewer will be available offering assistance in understanding the questionnaires if needed.
- 6) 3rd and 4th grade classrooms in each school will be randomly and evenly allocated to the interventions included in the study using computer-generated randomization application.
- 7) The researcher will be blinded of the classrooms of each school during the randomization process.
- 8) The researcher will be blinded of the names of the participants or their personal data during and after the questionnaire session.
- 9) After the questionnaire is finished, the researcher will then begin his educational lesson using electronic aids like a projector inside the classrooms or using Microsoft teams during the online session.
- 10) Another questionnaire will be distributed after the educational lesson for both session types to assess the post-session knowledge and practice in the participants.
- 11) A comparison will be carried out for the results of each question in both questionnaires and for the final results of both questionnaires to determine the statistical significance of both results.
- 12) These statistical results will be done by a separate statistician outside the study field and blinded from all the procedures.

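### The protocol's only named test is the before-to-after change within each intervention; the main analysis should instead compare post-session scores between arms, adjusted for the pre-session score and accounting for classroom.

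*Protocol*

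**What the plan says.** In the Protocol, section 4, Sample size calculation, the basis is given as follows: "Sample size estimation was based on testing the change in KAP before and after each educational intervention". The inputs are alpha 0.05, a beta "level of 0.1 (power = 90%), allocation ratio of 1:1", and a standardised effect d of 0.2. The result is stated as "The predicted sample size was found to be 265 children for each intervention", and then "After adding a 20% increase to adjust for dropout, the final sample size was 318 children for each intervention".

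Study procedures, step 4, gives a questionnaire before the sessions "to assess the pre-session knowledge and practice of the participants". Step 10 adds the second measurement: "Another questionnaire will be distributed after the educational lesson for both session types". Step 11 describes the analysis: "A comparison will be carried out for the results of each question in both questionnaires and for the final results of both questionnaires". Step 6 randomises classrooms within each school.

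The primary objective is to compare online with conventional education on knowledge and on practice. The outcome in the research-question framing is an improvement in both, with no metric. Section 6, Statistical analysis, names no method. Nothing in the protocol mentions adjustment for the pre-session score.

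**The concern.** The objective concerns the difference between two teaching methods. The sample size sentence and step 11 both describe a comparison of one questionnaire with the other, before against after. A within-arm change does not answer the objective. Both arms can improve significantly while one method is clearly better, and any gain from seeing the questionnaire a second time counts as improvement in either arm.

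If the before-to-after change is then carried into a between-arm comparison, as its use in the sample size suggests, the baseline enters with a fixed slope of 1. When the pre/post correlation is below 1, that slope is too steep. It adds noise, and it over-corrects any chance difference at baseline, so that the arm that starts lower tends to show the larger gain. Whole classrooms are allocated, so baseline balance depends on the number of classrooms more than on the number of children.

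At stake are the precision of the online-versus-conventional estimate, and whether the stated 90% power refers to the question that the trial asks.

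**Working it through.** **Inputs.** From the Sample size calculation: alpha 0.05 (sidedness not stated), power 90%, d = 0.2, 265 per arm, 318 after the dropout allowance. The pre/post correlation r, the ICC, the number of classrooms and the size of the trial's classes are not given. They are assumed below and shown as ranges.

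**1. The plan's own figure.** Paired t-test on the change, exact noncentral t, d = 0.2 in SDs of the change, 90% power:

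- two-sided: n = 265, as stated (normal approximation (1.960 + 1.282)² / 0.2² = 263);
- one-sided: n = 216.

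Then 265 × 1.2 = 318, as stated. The two-sample versions do not reproduce 265: two-sided 526 per arm (exact t 527), one-sided 429. An allocation ratio plays no part in a paired test, so its mention does not turn the figure into a between-arm calculation.

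**2. Between-arm comparison of raw change.** With a difference of 0.2 SD of the change and independent children, n per arm = 2 × (1.960 + 1.282)² / 0.2² = 526. Power is 63.4% at 265 per arm, and 71.3% at 318 if nobody drops out.

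**3. Adjusted post-session score against raw change.** With equal pre and post SDs s:

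- Var(change) = 2s²(1 − r);
- Var(post adjusted for pre) = s²(1 − r²);
- ratio = (1 + r)/2, which is below 1 for every r below 1.

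For the same difference of 0.2 SD of the change, with independent children:

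| assumed r | variance ratio | reduction | n per arm for 90% | power at 265 | power at 318 |
|---|---|---|---|---|---|
| 0.3 | 0.65 | 35% | 342 | 81.5% | 87.9% |
| 0.5 | 0.75 | 25% | 395 | 75.8% | 82.9% |
| 0.7 | 0.85 | 15% | 447 | 70.4% | 78.1% |
| 0.8 | 0.90 | 10% | 473 | 68.0% | 75.8% |
| 0.9 | 0.95 | 5% | 500 | 65.6% | 73.5% |

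**4. Baseline imbalance.** If the arms differ by D at baseline and the true effect is τ, the expected difference in change is τ + rD − D = τ − (1 − r)D. Adjustment with slope r removes the D term for the measured score, provided that the slope between classrooms equals the slope between children.

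How large D may be depends on quantities that are not in the protocol. As an illustration, the standard error of D in SDs of the score is √(2 × (ICC + (1 − ICC)/m)/k), with k classrooms of m children per arm. The Background mentions classes of 40 in Egypt generally. With m = 40, k = 318/40 ≈ 8:

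- ICC 0.02: 0.105;
- ICC 0.05: 0.136;
- ICC 0.10: 0.175.

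With m = 20, k = 16 and ICC 0.05 it is √(2 × (0.05 + 0.95/20)/16) = 0.110.

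**The case against.** The strongest reply is that the protocol fixes no between-arm analysis. The quoted sentence is the basis of a sample size, the outcome is named without a metric, and section 6 leaves the method to a statistician. Baseline adjustment is ordinary content of a statistical analysis plan, which may exist and is not shown.

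Much of this stands. A reader might infer that raw change is the trial's defined endpoint for comparing the arms, but the protocol does not say so, and the 265 belongs to a within-arm test. The absence of a named adjusted model is also no error in itself. The reply does not dispose of the point, though. The only test and the only comparison that the protocol does describe are before against after, and these do not directly answer its own primary objective. If an analysis plan specifies an adjusted between-arm comparison, the sample size sentence still has to be brought into line with it.

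A second reply is that randomisation keeps the between-arm difference in change unbiased on average, with chance imbalance already part of its standard error. That is correct. The argument is about precision, and about the result in the one trial that will be run, not about long-run bias.

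A third reply is that the size of the gain rests on assumptions. That is also correct. The variance figures treat children as independent, the gain shrinks to 5% at r = 0.9, and the classroom-level correlation may differ from the child-level one.

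**Conclusion.** The point holds as a recommendation to state the main analysis and to align the sample size with it. The protocol sizes the trial for change within each intervention, while its objective is a comparison between interventions. With the same d, a between-arm comparison of raw change has 63% power at 265 per arm before clustering. Adjusting for the pre-session score lowers the variance by 35% to 5% for r from 0.3 to 0.9, assuming equal SDs and independent children. Power at 265 then lies between 82% and 66%. That is a gain at almost no cost, but over this range it does not reach 90% at 265, nor at 318.

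Two further inferences go too far. A reader might conclude that adjustment removes chance imbalance between the arms. It reduces the effect of imbalance in the measured score only, and it is no substitute for an analysis that respects classroom allocation. A reader might also conclude that only a few classrooms are randomised. The protocol gives no number: 636 children would be about 16 classes of 40 or 32 of 20, and the 40 comes from general background, not from the two trial schools.

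**What to change.** State in section 6, or in the analysis plan with a pointer from section 6:

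- The main analysis compares the post-session knowledge score between arms, and separately the practice score, adjusted for the same child's pre-session score and for school. Classroom is accounted for as the unit of allocation, for example with a random classroom effect.
- Say which post-session measurement this refers to, since the research-question framing also lists follow-up every three months.
- Raw within-arm change is reported descriptively only.

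Replace the sample size sentence with one that refers to this comparison, and restate the power for the planned 318 per arm. Give the assumed r, the number and size of classrooms, and the ICC.

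Add an anonymous child code that links the pre- and post-session forms. Step 8 keeps names from the researcher and the protocol describes no such code, but the paired test behind the 265 already needs one, so this is no new burden.

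The cost is a few sentences, one repeated power calculation and a code on each form. No additional measurement is needed. If the restated power is judged too low, the sample size is a separate decision.

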**Framing the research question - PICOTS:**

P (participants): Primary school children of ages 7-9 years old in Egypt.

I (intervention): Online oral health education.

C (comparator): Conventional oral health education.

O (primary outcome): Improving the oral hygiene knowledge and practice in primary school children.

T (Time of follow up): Every 3 months interval for one academic year.

S (Study settings): 2 schools will be chosen (Al Rehab city and Al-Sherook city). The rationale behind choosing those two schools is to increase the sample size. Classrooms of grade two and grade three stages inside each school will be divided blindly into two groups; one receives the online oral health education while the other receives the conventional oral health education. Both schools had received simplified conventional oral health education service two years ago. The participants were of 5-6 years of age by then.

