**4. Methods:**

- **Study design:** Randomized controlled trial (RCT)
- **Study settings:** 2 schools will be chosen (Al Rehab city and Al-Sherook city). The rationale behind choosing those two schools is to increase the sample size. Classrooms of grade three and grade four stages inside each school will be divided blindly into two groups; one receives the online oral health education while the other receives the conventional oral health education. Both schools had received simplified conventional oral health education service two years ago. The participants were of 5-6 years of age by then.
- **Study population:** Grade three and grade four Egyptian students aged 7-9 years old situated in 2 different schools related to Futures Educational Systems in Egypt.

Inclusion criteria	Exclusion criteria

 
• 2nd and 3rd grade Egyptian students.
 
• Average of age 7-9 years old.
 
• Currently residing in Egypt.
 
• Both male and female students.
 
	
 
• Those who do not consent to participate in the study.
 
• Those who cannot speak English or Arabic.
 
• Non-Egyptians.
 

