**5. Data management:**

Data for each classroom will be collected through laptops (Google forms) or printed questionnaires, according to the nature of the session delivered. Results will be monitored and inserted into an excel sheet.

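### Classrooms are randomised, but the sample size treats children as independent, so the stated 90% power is too high for any positive classroom correlation

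*Protocol*

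**What the plan says.** The unit of allocation is the classroom. Study procedures, step 6, says that 3rd and 4th "grade classrooms in each school will be randomly and evenly allocated to the interventions included in the study using computer-generated randomization application". The Study settings entry under 4. Methods agrees: "Classrooms of grade three and grade four stages inside each school will be divided blindly into two groups". The PICOTS entry has the same structure but names different grades: "Classrooms of grade two and grade three stages inside each school will be divided blindly into two groups". The lesson is also delivered by session, with a projector in the classroom or over Microsoft Teams (Study procedures, step 9).

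The Sample size calculation section works in children. It begins: "Sample size estimation was based on testing the change in KAP before and after each educational intervention". With alpha 0.05, 90% power and d = 0.2, it reports: "The predicted sample size was found to be 265 children for each intervention". It continues: "After adding a 20% increase to adjust for dropout, the final sample size was 318 children for each intervention", for a total of 636. The section gives no ICC, design effect, class size or number of classrooms. The study design is described only as a randomised controlled trial.

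**The concern.** Children in one class share the lesson, the questionnaire sitting and the interviewer's help, so their changes in score are likely to be correlated. Each further child in a class then adds less information than an independent child would. The precision per intervention is that of 265 / [1 + (m − 1) × ICC] independent children, where m is the number of evaluable children per class.

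If the 265 assumes independence, a reader who takes the 90% at face value overestimates what the trial can detect. The research question asks whether online education is as effective as conventional education. A non-significant result from an underpowered trial could then be misread as evidence that the methods do not work or do not differ.

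**Working it through.** **Inputs from the protocol (Sample size calculation):** alpha 0.05, power 90%, d = 0.2, 265 per intervention, 318 after the dropout increase. The test and its sidedness are not named.

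**Assumed inputs:** m of 20 to 40 evaluable children per class, and ICC of the change score from 0.01 to 0.10. The protocol gives neither for the two schools. Its Background says only that Egyptian classrooms can reach 40 students or more.

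**Step 1: reproduce 265.** Paired t-test, two-sided, noncentral t with noncentrality 0.2 × √n and n − 1 degrees of freedom:
- n = 264: power 89.93%
- n = 265: power 90.04%

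So 265 is the smallest n that reaches 90%. The alternatives do not fit: one-sided paired gives 216, and a two-sided two-sample t-test needs 527 per arm. The dropout step is 265 × 1.2 = 318. No part of either figure allows for clustering.

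**Step 2: add the design effect.** DE = 1 + (m − 1) × ICC and n_eff = 265 / DE. Power comes from the noncentral t with noncentrality 0.2 × √n_eff. The degrees of freedom are n_eff − 1 (no penalty) or k − 1 with k = 265 / m classrooms (with penalty). For m = 25, k = 10.6:

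| ICC | DE | n_eff | Power, no penalty | Power, with penalty |
|---|---|---|---|---|
| 0 | 1.00 | 265 | 90% | – |
| 0.01 | 1.24 | 214 | 83% | 75% |
| 0.02 | 1.48 | 179 | 76% | 67% |
| 0.05 | 2.20 | 120 | 59% | 51% |
| 0.10 | 3.40 | 78 | 41% | 36% |

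From m = 20, ICC 0.01 to m = 40, ICC 0.10, DE runs from 1.19 to 4.90, n_eff from 223 to 54, and power from 84% to 30% without the penalty or 78% to 23% with it.

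A simulated t-test on classroom means of change (20,000 runs, 11 classes of 24) agrees with the penalised column: 67.9%, 51.2% and 36.0% at ICC 0.02, 0.05 and 0.10, with 5.1% rejection under the null.

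**Step 3: allow for classes shrinking with dropout.** If 318 recruited in classes of 25 fall to 265, then m = 25 × 265 / 318 ≈ 20.8. At ICC 0.05, DE = 1 + 19.83 × 0.05 = 1.99, and power is 63% without the penalty or 56% with it.

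**Step 4: could the 20% absorb the clustering?** With no dropout at all, 318 / 265 = 1.20 is the largest design effect covered. The break-even ICC is 0.20 / (m − 1): 0.0105, 0.0083 and 0.0051 at m = 20, 25 and 40. At m = 25 and ICC 0.05, 318 analysed children give 67% before the penalty.

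**Step 5: the comparison between methods.** Two-sample t-test, 265 per arm, d = 0.2, independent children: 63%. With noncentrality 0.2 × √(n_eff / 2) and 2k − 2 degrees of freedom, power runs from 53% (m = 20, ICC 0.01) to 16% (m = 40, ICC 0.10).

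**The case against.** **The test is inferred.** The protocol names no test, and its parameter list ("power = 90%), allocation ratio of 1:1, to detect an effect size" d of 0.2) includes an allocation ratio, which a one-group paired calculation does not use. This is fair, but the exact match and the before-and-after wording make the inference strong. The missing clustering allowance does not depend on which t-test was used.

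**The relevant ICC may be small.** Stable differences between classes cancel in a pre/post change, so the ICC of the change score may be below that of raw scores. At ICC 0.005 and 20 to 25 per class, power without the penalty is still about 87%. This stands as a limit on the size of the loss, not its direction: classes can still differ in how they respond to a lesson given to the whole class. Stratifying allocation by school or grade could also remove some between-class variance, but the sample size section claims no such offset.

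**The extremes are stretched.** Forty evaluable children per class implies 40 × 318 / 265 = 48 recruited if dropout occurs as planned. With 40 recruited and about 33 evaluable, the worst case at ICC 0.10 is 34% without the penalty and 28% with it. If all 318 were analysed at 25 per class, ICC 0.01 gives 89% and ICC 0.02 gives 83% (83% and 77% with the penalty). Both points stand: the 40-per-class row is an outer bound, and at very small ICC with little dropout the shortfall is modest.

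**Analysis belongs in the SAP.** The choice of model does, and no claim is made here about type I error, since the protocol names no between-arm test. The sample size and its 90% power, however, are stated in the protocol and conflict with the protocol's own allocation.

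**Conclusion.** The concern holds. The 90% belongs to a trial of independent children, and this trial allocates classrooms. The direction is certain for any positive ICC of the change score at the planned 265 evaluable children. The size cannot be fixed from the protocol. With 25 evaluable per class and ICC 0.01 to 0.10, both assumed, power for the before/after test is 83% to 41%, or 75% to 36% with degrees of freedom based on the number of classrooms. The dropout allowance does not rescue the claim unless dropout is nil and the ICC is about 0.01 or lower.

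The 90% also never applied to the stated primary objective and null hypothesis, which compare the two methods. That comparison starts from 63% at d = 0.2 before clustering is considered.

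**What to change.** 1. In 4. Methods, describe the trial as cluster-randomised by classroom.
2. In Sample size calculation, replace the 90% with power computed using 1 + (m − 1) × ICC over a stated ICC range (for example 0.01 to 0.10), with the actual class sizes and the number of classrooms left after the two pilot classes are removed. Report it for the between-method comparison as well as the within-method change.
3. If 90% is to be kept, restate the number of classrooms. At 25 per class and ICC 0.01, 0.02, 0.05 and 0.10, before any degrees-of-freedom penalty or dropout, the evaluable children needed per intervention are:
   - within-method change, 265 × DE: 329, 393, 583 and 901;
   - between-method comparison at d = 0.2, 527 × DE: 654, 780, 1,160 and 1,792.

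   Meeting only the first set would leave the between-method comparison at about 63% at best.
4. State that the between-method comparison accounts for classroom, for example by a random classroom intercept with small-sample degrees of freedom or an analysis of classroom means. The details can sit in the SAP.
5. Record a classroom identifier with each questionnaire. Section 5 already says "Data for each classroom will be collected through laptops" or printed forms, so this adds one field.

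The cost is a recalculation, some wording and that field. The stated power falls and intervals widen. No extra children are needed if the lower power is accepted; keeping 90% would need more classrooms and possibly another school.

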### **Study procedures:**

- 1) A literature review was conducted using electronic search engines like PubMed and Google scholar to identify studies assessing the effect of online and conventional oral health education on improving the oral health knowledge and practice in school children regarding their oral hygiene.
- 2) After reviewing many articles, a questionnaire was selected to assess the above outcomes. The questionnaire was chosen according to availability and effectiveness, and it was modified by simplifying and deselecting some of the questions that aren't related to the age group to better suit the age group of question.
- 3) A piloting session will be done on two separate classes, one from each educational stage to assess the modified questionnaire in terms of ease of understanding and comprehension to the participants. Those two classes will not be included in the final results of the study.
- 4) The questionnaire will be distributed before conducting the oral health education sessions (both online and conventional) to assess the pre-session knowledge and practice of the participants.
- 5) All questionnaires are self-administered but a well-trained interviewer will be available offering assistance in understanding the questionnaires if needed.
- 6) 3rd and 4th grade classrooms in each school will be randomly and evenly allocated to the interventions included in the study using computer-generated randomization application.
- 7) The researcher will be blinded of the classrooms of each school during the randomization process.
- 8) The researcher will be blinded of the names of the participants or their personal data during and after the questionnaire session.
- 9) After the questionnaire is finished, the researcher will then begin his educational lesson using electronic aids like a projector inside the classrooms or using Microsoft teams during the online session.
- 10) Another questionnaire will be distributed after the educational lesson for both session types to assess the post-session knowledge and practice in the participants.
- 11) A comparison will be carried out for the results of each question in both questionnaires and for the final results of both questionnaires to determine the statistical significance of both results.
- 12) These statistical results will be done by a separate statistician outside the study field and blinded from all the procedures.

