**Objectives:**

➤ **Primary objective :**

- To compare the online oral health education to the conventional oral health education regarding :
  1. Oral health knowledge of primary school children of 7-9 years old.
  2. Assessing oral hygiene measures practice in primary school children of 7-9 years old.

➤ **Secondary objective :**

Is to evaluate the efficacy of a new oral health education method to deliver health information to target population

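### Practice, one of two primary outcomes, is read from a post-lesson form with no stated interval, so its answers cannot be told apart from recall of the lesson

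*Protocol*

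**What the plan says.** The protocol treats practice as primary in two places. The PICOTS outcome is "Improving the oral hygiene knowledge and practice in primary school children". The second of the two items under the primary objective is "Assessing oral hygiene measures practice in primary school children of 7-9 years old".

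Study procedures describes the measurement. Step 4 gives a questionnaire before the education sessions, covering knowledge and practice. Step 9 then says "After the questionnaire is finished, the researcher will then begin his educational lesson". Step 10 says "Another questionnaire will be distributed after the educational lesson for both session types to assess the post-session knowledge and practice in the participants". Step 11 compares the two questionnaires question by question and also "for the final results of both questionnaires to determine the statistical significance". On how the forms are completed, step 5 says "All questionnaires are self-administered but a well-trained interviewer will be available offering assistance in understanding the questionnaires if needed". No observed or clinical measure of practice is described.

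The PICOTS line on timing gives follow-up as "Every 3 months interval for one academic year". No step in Study procedures refers to it.

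**The concern.** Knowledge can change during a lesson, and a form completed directly afterwards can measure that. Practice is what a child does at home from day to day, and it can change only over time. If the second form follows the lesson directly, a practice item on it has three possible sources: what the child already did, what the child now intends, or what the child has just been told is right. The form cannot separate them.

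At stake is the practice half of the primary objective. A gain from the first form to the second, or a difference between online and conventional teaching, could be reported as an effect on practice when no opportunity for changed practice had been observed. An analysis plan could not repair this later, because the missing element is a measurement taken after an interval.

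**Working it through.** The point rests on the order and timing of the forms, so the check is mainly a comparison of sections.

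**1. The plan's own figure.** The Sample size calculation section rests on change in KAP before and after each intervention, with d = 0.2, α = 0.05 and power 90%. The normal approximation for a two-sided paired test is n = (1.960 + 1.282)² / 0.2² = 10.51 / 0.04 = 262.7, so 263. The exact noncentral-t calculation gives 265, which is the stated number. Adding 20% gives 265 × 1.2 = 318 per intervention, and 2 × 318 = 636 in total. The figures reproduce. The time between the two forms is not an input, so the calculation does not show when the second form is given.

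**2. What the procedures fix about timing.**
- First form to lesson: fixed by step 9. The lesson begins when the form is finished.
- Lesson to second form: step 10 says only that the form comes after the lesson and is post-session. No number of days, weeks or months is given.
- Number of forms: step 11 refers to both questionnaires, that is, one before and one after. No third form appears.

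**3. What ties the second form to the lesson.** Step 10 calls the measurement post-session, as step 4 calls the first one pre-session. Step 8 speaks of a single questionnaire session. The Data management section sets the medium, online form or paper, by the type of session delivered. Together these make form, lesson, form on one occasion the most natural reading.

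**4. What points to later measurement.** PICOTS states 3-monthly follow-up over an academic year. That implies repeated later assessments, whereas steps 10 and 11 describe one second form. The two sections do not match, and the protocol does not say which time point is primary for either outcome.

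**5. What a practice answer on the step 10 form can mean.** On the reading in item 3, there has been no occasion between the forms to practise anything differently. A changed answer is then compatible with recall or intention. An unchanged answer is compatible with stable habits, whether or not the lesson will later alter them. Neither answer bears on whether practice improved, and this is true in both arms.

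**The case against.** The strongest objection is that the protocol never says the second form is given on the same day. The gap between lesson and second form is left open, and three features fit later measurement: the follow-up line in PICOTS, a 20% dropout allowance, and a Timeline with eight months (January to August 2021) for data collection and entry. If the step 10 form is itself the form given at a 3-monthly follow-up, the problem disappears. That stands as a possible reading, and the point must not be put as though same-session measurement were stated. It does not remove the need for a change. Dropout and a long collection period also fit a programme staggered over many classrooms, and a single second form does not match a repeated 3-monthly schedule. If an interval was intended, step 10 has to give it.

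A reader might also infer three stronger claims that the documents do not support:

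- **That every change in a practice answer is artefact, or that true change is zero by construction.** With no interval printed, the most that can be said is that such answers cannot be distinguished from recall, intention or earlier habits.
- **That adding practice items dilutes a total score and costs a calculable amount of power.** The protocol gives no scoring rule or weights and does not say that knowledge and practice are summed. Step 11 also compares each question separately, and d = 0.2 is assigned to KAP as a whole. Any power figure would rest on assumed weights, variances and correlations. The direction is open as well: items that cannot move would shrink a total change, and repeated taught answers would enlarge it.
- **That the comparison between arms is biased.** The two arms are measured on the same schedule, and nothing in the text shows that recall would differ between them. The defect is in what the answers mean.

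**Conclusion.** The concern holds in a limited form. Practice is one of two primary outcomes, yet the only post-lesson measurement in the procedures is a self-administered form tied to the session. Followed as written, a difference in step 11 on practice items would not show a difference in practice. The follow-up in PICOTS could supply a usable measurement, but no procedure step implements it.

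The conclusion rests on reading steps 8 to 10 as one occasion, which is the natural reading but is not stated. It would fall away if the sponsor confirmed that the step 10 form is given at a 3-monthly follow-up. The extent is one of the two items in the primary objective. The knowledge item is not affected by this point, and no figure for bias or lost power can be derived from the protocol.

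**What to change.** In Study procedures:

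- **Step 10:** state when the second form is given relative to the lesson. If it is given at the session, use it for knowledge only, by omitting the practice items or leaving them unscored.
- **New step:** implement the follow-up stated in PICOTS and name one 3-monthly time point as the one for practice. Give the practice items there.
- **Step 11:** score practice separately from knowledge and compare the arms on it at the named time point. Keep the post-session comparison for knowledge.
- **If no later form will be given:** draw no conclusion on practice, and say so where the primary outcome is defined.

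If the step 10 form was always meant to be a follow-up form, it is enough to state the interval there, name the time point, and make PICOTS and Study procedures agree.

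The cost is small. The same-day form becomes shorter, there is no same-day practice result, and at least one later questionnaire has to be run, which the stated follow-up already implies. A later form would still be self-reported, so it removes the timing problem but not the general limits of self-reported behaviour.
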